6.2.3. Incidence and Severity of TEAEs as Assessed by the CTCAE

See safety [Section 6.6.1](#).

6.3. Exploratory Endpoints

6.3.1. PK Parameters

Exploratory PK parameters will not be measured/reported due to study termination.

6.3.2. Incidence of Development of ADA During the Study

Participants positive for ADA (screening, confirmatory, specificity and titer) will be summarized by treatment group and timepoint with number and percent for SAS.

6.3.3. Change in Magnitude of IL-2 Response pre- and post-GC in Peripheral Blood from Baseline to GC at Weeks 12, 24, and 36

These endpoints will not be measured/reported due to study termination.

6.3.4. Change in Magnitude of IL-2 Response pre- and post-GC in Peripheral Blood from GC at Day 15 to GC at Weeks 12, 24, and 36

These endpoints will not be measured/reported due to study termination.

6.3.5. Change in circulating levels of various biomarkers from pre-dose to post-dose on Day 1, 4, and 7

These endpoints will not be measured/reported due to study termination.

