1.3.2. Part B (Phase 2 – Double-Blind)

Visit Identifier	Screen	Run-in		Treatment Period			GC	FU	GC	GC	GC	FU	ET	Notes
Abbreviations used in this table may be found in Appendix 13 .	Day -49 to Day -22 (fasted)	Day -21 (fasted)	Day -20 to Day -1	Day 1 (fasted)	Day 4	Day 7	Day 15 (fasted)	Day 28	Day 84 (fasted)	Day 168 (fasted)	Day 252 (fasted)	Day 364		
 Day relative to start of study intervention (Day 1). Run-in is a 1-day GC visit and must be at least 21 days prior to Day 1.
Visit Window		-3 d						±3 d	±5 d	±5 d	±5 d	±3 d		
 See Section 8.4.3 for follow-up AE and SAE assessments.
Screening Assessments														
 All screening should be done ≥21 days and ≤49 days before the first dose.
Informed consent	X													
 Informed consent should be obtained prior to undergoing any study-specific procedures. See Section 10.1.3 for additional information.
Demographics and medical history	X													
 Includes disease history (symptoms at diagnosis and length of time on GFD).
Review eligibility criteria	X	X		X										
HIV, HBV, HCV testing	X													
HLA genotype and CeD serology	X													
 All participants will be assessed via central laboratory for HLA genotype and CeD serology (eg, tTG-IgA and DGP-IgG) at screening to confirm eligibility prior to screening GC. For rescreening: HLA does not need to be repeated and CeD serology only needs to be repeated if >3 months have elapsed from last assessment.
12-Lead ECG	X													
 Not required for participants who have had an ECG within 12 weeks prior to screening.
Clinical Procedures														
Physical examination	X											X	X	
 See Section 8.3.1 for additional information.
Vital signs	X	X		X	X	X	X	X	X	X	X	X	X	
 See Section 8.3.2 for additional information. Includes weight and height at screening only.
Contraception check	X	X		X	X	X	X	X					X	

090177e19fcc12ed\Approved\Approved On: 30-Jan-2024 19:45 (GMT)

090177e19fcc12ed\Approved\Approved On: 30-Jan-2024 19:45 (GMT)

Visit Identifier	Screen	Run-in		Treatment Period			GC	FU W4	GC W12	GC W24	GC W36	FU W52	ET	Notes

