4.2. Scientific Rationale for Study Design

In KAN-101-01 study, participants treated with 0.15 mg/kg, 0.3 mg/kg and 0.6 mg/kg of KAN-101 exhibited T-cell tolerance to gliadin by demonstrating minimal change or a decrease in the gliadin-specific T-cell response to GC compared to participants in the placebo

who exhibited an increase in the gliadin-specific T-cell response following GC. In addition, participants treated with 0.6 mg/kg KAN-101 exhibited lower median interleukin-2 (IL-2) levels after GC compared to the IL-2 levels in Placebo or 0.15 mg/kg and 0.3 mg/kg KAN-101 groups. Overall, KAN-101 demonstrated an acceptable safety and tolerability profile in both Part A and Part B of the study at all doses tested. There were no deaths, SAEs, Grade 3 TEAEs, or DLTs observed; therefore, no MTD was determined in this study. With expected efficacy dose of 1.2 mg/kg or over, higher doses may be explored in future studies. Further details are provided in the KAN-101 IB.

In KAN-101-01 and non-clinical models, T-cell tolerance induction was observed as early as 1 week after drug administration in celiac patients, supporting the timing of the primary endpoint assessment and the safety review period.

In the previous protocol for this study, 1.2 mg/kg, 3.0 mg/kg and 6.0 mg/kg KAN-101 were planned to be evaluated in a MAD 3+3 design (Part A). Based upon emerging data from Part A, the protocol has been amended to proceed to Part B following completion of Part A 3.0 mg/kg dose cohort. The decision not to test 6.0 mg/kg was not due to any safety concerns or exposures which exceeded the NOAEL. Part B evaluated 0.6 mg/kg, 1.2 mg/kg, and 3.0 mg/kg in a dose-ranging design (Part B) in CeD participants on GFD

Sixteen participants were randomized at which time, study was paused and ad-hoc DSMB was convened to assess emerging safety data.

After review of emerging data by DSMB, Part B was closed due to concerns for sensitization by screening GC, potentially leading to higher frequency and severity of AEs observed after dosing with KAN-101/PBO. The study remains blinded.

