8.2.2. Plasma IL-2 Biomarker Assessment

Plasma samples will be collected to assess the magnitude of biomarker response of IL-2 pre- and post-GC in peripheral blood (Part A – exploratory endpoint; Part B and Part C – primary endpoint on Day 15 and secondary endpoints on Weeks 12, 24, and 36).

Further details are presented in [Section 8.7](#).

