1. VERSION HISTORY

This Statistical Analysis Plan (SAP) for study KAN-101-02 Part B is based on the protocol amendment dated 30Jan2024.

Table 1. Summary of Changes

Version/Date	Associated Protocol Amendment	Rationale	Specific Changes
1 28OCT2022	Original 31Aug2022	Not Applicable (N/A)	N/A
2 10Jul2023	Amendment 1 21Jun2023	Protocol amended	In Section 2.3, study drug arms are defined as 0.6 mg/kg, 1.2 mg/kg, and 3.0 mg/kg as active study drug arms and placebo in Part B
28Feb2024	Amendment 3 30Jan2024	Protocol amended	
Section 2 and Section 2.3, Part C was added, Figure 1 was updated.
 
Section 2.2 Table 2 and Section 2.2.1, estimand 1 was changed to treatment policy, estimand 2 was removed.
 
Section 3.1 and Section 3.3, some editorial changes.
 
Section 5.1 was updated to reflect that there is no hypothesis testing for Part B.
 
Section 5.1 was removed. No analysis for continuous endpoints.
 
Section 6.1 was updated to reflect that only descriptive summary will be performed for the primary endpoint.

Table 1. Summary of Changes

Version/Date	Associated Protocol Amendment	Rationale	Specific Changes
			
Main analysis and sensitivity analysis were removed for the primary endpoint.
 
Sections 6.3.3, 6.3.4, 6.3.5 (old Sections 6.4.3, 6.4.4, 6.4.5 in version 2), analysis was removed.
 
Section 6.6 (old Section 6.7), listings and/or summaries for participants impacted by COVID-19 were removed.
 
Section 7, Interim analysis was removed.
 
Appendix 1, Analysis related items were removed.
 
Appendix 2.1, analysis windows were added for Immunogenicity data (Table 6).

13Jun2025	Amendment 3 30Jan2024	Study termination	Section 6.3 and Appendix 1, the exploratory endpoints (except section 6.3.2 Incidence of development of ADA during the study) will not be measured/reported.

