6.3.7. Biopsy Substudy

Biopsy substudy endpoints will not be measured/reported due to study termination.

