6.3.6.2. PGIS

PGIS and change from baseline will be descriptively summarized with number of observations, mean, SD, min, 1st, 2nd and 3rd quartiles, max for each treatment group by timepoint. The change from baseline will be analyzed using ANCOVA models in [Section 5.2.1](#) by timepoint. LSM of the treatments, LSM of the treatment difference with PBO, p-value and 95% CI will be generated.

Due to study termination, only descriptive summaries will be provided for data up to Week 12.

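### SAP Part B drops the Week 12–36 IL-2, PRO and biopsy summaries because of study termination, but by the documents' dates the Week 12–36 visits were due before any termination they point to

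*SAP*

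**What the plan says.** Protocol Section 4.2 (Amendment 3) reports on Part B in the past tense: "Sixteen participants were randomized at which time, study was paused and ad-hoc DSMB was convened to assess emerging safety data". It continues: "After review of emerging data by DSMB, Part B was closed due to concerns for sensitization by screening GC". The Part B schedule (Section 1.3.2) keeps challenges with IL-2 sampling at Weeks 12, 24 and 36, and the substudy biopsy at Week 52. Protocol Section 9.3.4 commits to descriptive summaries of the Week 12–36 IL-2 changes, the PROs and the Week 52 histology.

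The Part B SAP "is based on the protocol amendment dated 30Jan2024". Its 13 Jun 2025 revision gives study termination as the rationale and removes every exploratory endpoint except anti-drug antibodies:

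- Sections 6.3.3 and 6.3.4 (IL-2 at Weeks 12, 24 and 36): "These endpoints will not be measured/reported due to study termination".
- Section 6.3.6 (PROs): the same reason.
- Section 6.3.7: "Biopsy substudy endpoints will not be measured/reported due to study termination".

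The same SAP still reports ADA by timepoint (Section 6.3.2, with sampling listed to Week 52 in Section 3.3) and challenge completion at each scheduled challenge (Section 6.5.4). SAP Part C cancels Week 12 IL-2 (Sections 6.3.3 and 6.3.4) but keeps PROs: "Due to study termination, only descriptive summaries will be provided for data up to Week 12".

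Protocol Section 8.2.2 describes IL-2 in Parts B and C as "primary endpoint on Day 15 and secondary endpoints on Weeks 12, 24, and 36". The synopsis, Sections 3, 4.1.2 and 9.3.4, and the SAPs treat the later timepoints as exploratory.

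**The concern.** Part B was fully randomized before Amendment 3, so its follow-up calendar can be bounded from the documents. If the Week 12–36 visits fell before the study stopped, stopping the study is not a reason for those visits to have produced no data. The SAP does not say whether samples were taken, whether they were assayed, or why available results would go unsummarised.

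Durability of the IL-2 response is a stated Part B objective. Part B is also the only part with a pre-treatment challenge, so only there can later responses be compared with an untreated one. As written, the report would show how many participants completed each later challenge without showing the IL-2 result or accounting for its absence.

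**Working it through.** **Inputs**

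- All 16 randomized by 30 Jan 2024 (protocol Section 4.2; amendment date).
- Lag from randomization to Day 1: randomization falls between the run-in challenge and Day 1. Section 1.3.2 says "Run-in is a 1-day GC visit and must be at least 21 days prior to Day 1" and gives that visit a 3-day window, so the longest planned lag is 21 + 3 = 24 days. The latest Day 1 is then 30 Jan 2024 (no lag) to 23 Feb 2024 (24 days).
- Visits (Section 1.3.2): Day 84 ±5, Day 168 ±5, Day 252 ±5, Day 364 ±3.
- SAP Part B revision: 13 Jun 2025.

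**Reproducing the plan's figure.** 52 × 7 = 364, and Day 7 to Day 364 inclusive is 364 − 7 + 1 = 358 days, the follow-up length in Section 4.1.2.

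**Latest in-window date** = latest Day 1 + (visit day − 1) + upper window. Week 36 adds 251 + 5 = 256 days and Week 52 adds 363 + 3 = 366 days.

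| Visit | Day 1 = 30 Jan 2024 | Days before 13 Jun 2025 | Day 1 = 23 Feb 2024 | Days before 13 Jun 2025 |
|---|---|---|---|---|
| Week 12 | 27 Apr 2024 | 412 | 21 May 2024 | 388 |
| Week 24 | 20 Jul 2024 | 328 | 13 Aug 2024 | 304 |
| Week 36 | 12 Oct 2024 | 244 | 5 Nov 2024 | 220 |
| Week 52 | 30 Jan 2025 | 134 | 23 Feb 2025 | 110 |

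**Against the termination itself.** No termination date is given. The nearest pointer is SAP Part C version 3 (13 Dec 2024), which still specified Week 52 Marsh score output, so termination had probably not been decided by then. The last Week 36 visit falls 62 to 38 days before that date. The last Week 52 visit falls 48 to 72 days after it.

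**Sensitivity to late dosing.**

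- For a Week 52 visit to fall after 13 Jun 2025, Day 1 must be later than 12 Jun 2024, that is, more than 134 days after Amendment 3.
- For a Week 36 visit to fall after 13 Dec 2024, Day 1 must be later than 1 Apr 2024, more than 62 days after it.
- A 90-day delay puts Week 36 at 10 Jan 2025 and Week 52 at 30 Apr 2025, the latter still 44 days before the SAP revision.

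**Maximum data affected.** 16 × 3 = 48 challenge pairs (96 samples). Up to about 50% of 16, or about 8, biopsy pairs.

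**The same reason elsewhere.** SAP Part B Section 6.3.1 gives termination as the reason for dropping exploratory PK. Those parameters come from Day 1 and Day 7 samples, and the dose-normalised ones are just the still-reported AUC and Cmax divided by dose. Section 6.3.5 cancels Day 1, 4 and 7 biomarkers, which the protocol lists for Part C only. The reason appears to have been applied as a block and not endpoint by endpoint.

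**Part C.** SAP Part C Table 7 gives IL-2 and the symptom diary the same Week 12 window, Day 70 to 98. The diary result is kept and the IL-2 result is not.

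**The case against.** Much of the case on the other side stands.

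- A reader might infer that termination cannot explain the cancellation at all. That goes too far. The SAP wording covers measuring as well as reporting, and ending a programme can explain a decision not to assay stored plasma or produce exploratory tables after the visits have passed.
- Scheduled is not collected. Section 4.2 says sixteen were randomized, not that all were dosed, and the length of the pause is not given. Participants without three full doses have no later challenge or IL-2 sample (protocol Section 7.1). Biopsies were taken only at applicable sites. The 48 and 8 are ceilings.
- A termination between mid-December 2024 and February 2025 could have removed the last Week 52 visits.
- Protocol Section 9 lets the SAP change the plan, requiring an amendment only for major changes to the primary endpoint. Section 9.3.4 lets exploratory results be left out of the CSR. Section 8.2.2's secondary label is a lone outlier and does not take these endpoints out of that allowance.
- PROs need no assay, so keeping Week 12 PROs while dropping Week 12 IL-2 in Part C is not in itself a contradiction.
- With about four participants per arm and no testing, the summaries would be modest.

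What the objection leaves unanswered is the account itself. Permission to omit results does not make termination an accurate reason for data scheduled before it. SAP Part B Section 2.1, which lists departures from the protocol's plan, names only the analysis-set definitions, although the revision table does record the cancellation.

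**Conclusion.** The point holds in a limited form. By the documents' dates, the Week 12–36 visits of all 16 Part B participants were due by about October to November 2024 and Week 52 by about January to February 2025. Those are 7.2 to 8.0 months and 3.6 to 4.4 months before the SAP revision that cancels them. This assumes dosing within 24 days of 30 Jan 2024. Termination therefore does not by itself explain an absence of scheduled Week 12–36 data. For Week 52 the conclusion is weaker, because the termination date is unknown and the last visits may have been lost.

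A reader might infer selective reporting. The documents do not support that: they do not show that the later IL-2 samples were assayed or that anyone had seen Part B results by arm, and exploratory endpoints were cut in Parts A and C as well. The finding concerns an incomplete explanation and the unsummarised use of whatever data are in hand.

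**What to change.** 1. In SAP Part B Sections 6.3.3, 6.3.4, 6.3.6 and 6.3.7, summarise descriptively whatever IL-2, PRO and histology data were collected and are available: observed cases, FAS, by arm, with n at each timepoint.
2. In SAP Part C Sections 6.3.3 and 6.3.4, do the same for Week 12 IL-2, to match the PRO cut.
3. Where samples were not taken or not assayed, give the number and the actual reason, and state the termination date. New assays of stored plasma are not requested.
4. List the departure from protocol Section 9.3.4 in Section 2.1 of both SAPs.
5. As a minor point, align the tier in protocol Section 8.2.2 with the exploratory tier used elsewhere.

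The cost is a few descriptive tables and some explanatory text. SAP Part B Section 3.3 already defines the endpoints, and Part C Table 7 already sets the Week 12 window.

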6.3.6. PROs

PRO endpoints will not be measured/reported due to study termination.

6.3.7. Biopsy Substudy

Biopsy substudy endpoints will not be measured/reported due to study termination.

6.4. Subset Analyses

N/A

6.5. Baseline and Other Summaries and Analyses

6.5.1. Baseline Summaries

Demographic and baseline characteristics listed in [Section 3.4](#) will be summarized according to Sponsor's reporting standards for SAS.

6.5.2. Study Conduct and Subject Disposition

Participants evaluation, disposition, discontinuation will be summarized for SAS according to Sponsor's reporting standards.

6.5.3. Study Treatment Exposure

The exposure to study drug will be summarized by treatment group for number of doses of study intervention applied and number and percentage of participants who are compliant with the dosing regimen for SAS. A participant is considered compliant with the dosing regimen if he/she receives 80% to 120% of the expected amount of study intervention, in accordance with the protocol.

6.5.4. Gluten Challenge

GC will be summarized by number and percentage of participants completed GC at each GC scheduled timepoint for SAS.

6.5.5. Concomitant Medications and Non-Drug Treatments

Prior drug and non-drug treatment, concomitant drug and non-drug treatment will be summarized according to Sponsor's reporting standards.

6.6. Safety Summaries and Analyses

Safety analyses will be based on the SAS.

All clinical TEAEs, SAEs, withdrawal due to AEs, vital signs and safety laboratory data will be reviewed on an ongoing basis during the study to evaluate the safety of participants.

Safety data will be presented in tabular and/or graphical format and summarized descriptively, where appropriate. All safety endpoints will be listed and summarized in accordance with Sponsor's Standards. Categorical outcomes (eg, AEs) will be summarized by participant counts and percentage. Continuous outcome will be summarized using N, mean, median, SD, min, max. Participant listings will be produced for these safety endpoints accordingly.

6.6.1. Adverse Events

Adverse events will be summarized for SAS according to Sponsor's reporting standards for

- TEAEs
- Serious AEs (SAEs)

TEAEs will be summarized by the number of participants reporting any TEAE, system organ class (SOC), preferred term (PT), severity, relationship to investigational product.

CTCAE is used to grade the severity of AEs. TEAEs related to GC and infusion-related reactions (IRR) will also be summarized separately.

SAEs will be summarized by SOC and PT, and individual SAEs will be listed by participant.

A list of subjects who prematurely discontinue from the study due to an AE will be provided as well.

6.6.2. Safety laboratory Data

Clinical safety laboratory values and change from baseline and clinical significant change will be summarized according to Sponsor's standards.

6.6.3. Vital Signs

Vital signs and change from baseline and clinical significant change will be summarized according to Sponsor's standards.

7. INTERIM ANALYSES

No interim analysis is planned for Part B. DSMB will review unblinded safety and PK data periodically and make recommendations for study continuation as defined in the DSMB charter.

Appendix 1. Summary of Efficacy Analyses

Endpoint	Analysis Type	Population	Data Inclusion and Rules for Handling Intercurrent Events and Missing Data	Analysis Model
Change from baseline to Day 15 in IL-2 response	Summary	FAS	Observed cases, no imputation for missing data.	N/A

Appendix 2. Data Derivation Details

Appendix 2.1. Definition and Use of Analysis Windows in Reporting

Analysis windows will be used for PROs and vital signs, and laboratory tests.

If more than one observation from the same participant falls into the same analysis window, the value closest to the targeted day will be used as the observation for that visit. If two observations equally close to the targeted day, the later will be used. All observations will, however, be included in the listings.

Table 3. Analysis Windows for PGIS and PGIC

Visit Label	Targeted Day	Analysis window for data sets
Baseline (Screening up to first dosing date)	Day 1	Last observation up to and including first dosing date
Day 15	Day 15	Day 8 – Day 21
Week 4	Day 28	Day 22 – Day 56
Week 12	Day 84	Day 57 – Day 126
Week 24	Day 168	Day 127 – Day 210
Week 36	Day 252	Day 211 – Day 308
Week 52	Day 365	Day 309 – end of study

Table 4. Analysis Windows for Vital Signs

Visit Label	Targeted Day	Analysis window for data sets
Baseline (Screening up to first dosing date)	Day 1	Last observation up to and including first dosing date
Day 4	Day 4 pre-dosing	Day 2 - Day 4 pre-dosing
Day 7	Day 7 pre-dosing	Day 5 - Day 7 pre-dosing
Day 15	Day 15 pre-GC	Day 8 - Day 15 pre-GC
Day 28	Day 28 pre-GC	Day 16 – Day 28 pre-GC
Week 12	Day 84 pre-GC	Day 29 – Week 12 pre-GC
Week 24	Day 168 pre-GC	Week 12 GC +1 day – Week 24 pre-GC
Week 36	Day 252 pre-GC	Week 24 GC +1 day – Week 36 pre-GC
Week 52	Day 364	Week 36 GC +1 day – end of study

Table 5. Analysis Windows for Laboratory Tests

Visit Label	Targeted Day	Analysis window for data sets
Baseline (Screening up to first dosing date)	Day 1	Last observation up to and including first dosing date
Day 4	Day 4 pre-dosing	Day 2 - Day 4 pre-dosing

COPYRIGHTED MATERIAL [Redacted]

[Redacted]

[Redacted]

[Redacted]

[Redacted]

[Redacted]

[Redacted]

Appendix 2.3. Patient Global Impression of Severity (PGIS)

COPYRIGHTED MATERIAL [Redacted]

- [Redacted]
- [Redacted]
- [Redacted]
- [Redacted]
- [Redacted]

Appendix 2.4. Patient Global Impression of Change (PGIC)

COPYRIGHTED MATERIAL [Redacted]

- [Redacted]
- [Redacted]
- [Redacted]
- [Redacted]
- [Redacted]

090177e1a3cca9dd\Approved\Approved On: 06-Aug-2025 19:38 (GMT)

1. VERSION HISTORY

This Statistical Analysis Plan (SAP) for study KAN-101-02 Part C is based on the protocol amendment dated 30Jan2024.

Table 1. Summary of Changes

Version/Date	Associated Protocol Amendment	Rationale	Specific Changes
1 28Feb2024	Amendment 3 30Jan2024	Not Applicable (N/A)	N/A
2 05SEP2024	Amendment 3 30Jan2024	Added summary and analysis for Nausea Score and Vomiting Frequency and change from baseline	Sections 3.3 and 6.5.4.1, CDSD 1-Day, 3-Day, 7-Day Nausea Score and Vomiting Frequency and change from baseline at each timepoint post-gluten challenge will be summarized and analyzed using Wilcoxon Signed-rank test for within treatment paired comparison and Wilcoxon Rank Sum test for comparison between placebo vs each of KAN group.
3 13DEC2024	Amendment 3 30Jan2024	Made clarification for baseline, 3-day and weekly average calculation and timepoints. Marsh score is categorical	Sections 3.3 and 6.4.5.1, CDSD average score calculation and analysis timepoint were updated. Section 6.4.6.1, Screening and Week 52 Marsh score will be summarized with frequency and percentage. Change from screening to Week 52 will be summarized using shift table

Table 1. Summary of Changes

Version/Date	Associated Protocol Amendment	Rationale	Specific Changes
		Define IL-2 and CDS analysis window	Appendix 2.1, Table 7 was added for IL-2 and CDS analysis window.
4 13Jun2025	Amendment 3 30Jan2024	Study termination	Sections 6.3.1, 6.3.3, 6.3.4 and 6.3.5, 6.3.7 exploratory endpoints and biopsy substudy endpoints will not be measured/reported. Section 6.3.6, descriptive summary for PRO endpoints will be performed for data up to Week 12.

